2.1.4.4 Vital signs variables

Vital signs include blood pressure (mmHg), heart rate (beats per minute), respiratory rate (breaths per minute), body temperature (degrees Celsius) and body weight (kg) will be measured at every scheduled visit. Height (cm) will be measured at Visit 1 (Week 0) and Visit 10 (Week 52/EOT). Baseline values for vital signs will be the original baseline from the parent study.

2.1.4.5 Electrocardiogram variables

A standard 12-lead ECG will be performed at Visit 1 (Week 0), Visit 10 (Week 52/EOT), Visit 11 (Week 64/EOS) and/or early termination. ECGs were recorded automatically by the device at the Investigator site. Baseline values for ECG will be the original baseline from the parent study.

2.1.4.6 Physical examination

Physical examinations include an assessment of general appearance, skin, eyes, ear/nose/throat, heart, chest, abdomen, reflexes, lymph nodes, spine, and extremities, including menstruation status for girls, will be measured at Visit 1 (Week 0), Visit 5 (Week 12), Visit 8 (Week 24), Visit 10 (Week 52/EOT), Visit 11 (Week 64/EOS) and/or early termination. The overall assessment, 'Normal' or 'Abnormal', will be provided by investigator. In case of clinically significant findings, corresponding AE should be reported in adverse event eCRF form.

2.1.5 Pharmacokinetic variables

The pre-dose serum PK sampling will be collected at Visit 1 (Week 0), Visit 5 (Week 12), Visit 8 (Week 24), Visit 10 (Week 52/EOT), Visit 11 (Week 64/EOS) and/or early termination. The baseline values for PK variables are the original baseline from the parent study.

2.1.6 Immunogenicity variables

Samples for anti-drug antibodies (ADAs) are collected at Visit 1 (Week 0), Visit 5 (Week 12), Visit 8 (Week 24), Visit 10 (Week 52/EOT), Visit 11 (Week 64/EOS) and/or early termination. In case of suspected anaphylaxis or systemic hypersensitivity reaction, sample for ADA should be

obtained as close to the time of the event as possible. The baseline used to define ADA variables refers to the baseline value in the parent study.

The immunogenicity variables include ADA status (positive or negative) and titer as follows:

- Number of patients with ADA negative

ADA negative is defined as ADA assay is negative at all times or exhibit a pre-existing immunoreactivity.

- Number of patients with ADA positive

ADA positive is defined as either treatment-boosted or treatment-emergent response in the ADA assay.

- Number of patients with pre-existing immunoreactivity.

Pre-existing immunoreactivity is defined as either an ADA positive response in the assay at baseline of the parent study with all post first dose ADA results negative in the current study, or an ADA positive response at baseline of the parent study with all post first dose ADA results in the current study less than 4-fold of the baseline titer levels of the parent study.

- Number of patients with treatment-emergent response in the ADA assay.

Treatment-emergent response is defined as a positive response in the ADA assay post first dose in the current study, when baseline status in the parent study is negative or missing. The treatment-emergent response is further characterized as:

- Persistent response - defined as a treatment-emergent ADA positive response with two or more consecutive ADA positive sampling time points separated by greater than 12-week period (greater than 84 days), with no ADA negative sample in between,
- Indeterminate response - defined as a treatment-emergent response with only the last collected sample positive in the ADA assay,
- Transient response - defined as a treatment-emergent ADA positive response that is not considered persistent or indeterminate.

- Number of patients with treatment-boosted response in the ADA assay.

Treatment-boosted response is defined as a positive response in the ADA assay post first dose in the current study that is greater than or equal to 4-fold of the baseline titer levels of the parent study, when baseline status of the parent study is positive.

- Titer values (titer value category):

- Low (titer <1,000),
- Moderate (1,000 ≤ titer ≤10,000),
- High (titer >10,000).

- ADA positive samples will be further characterized for the presence of neutralizing antibody (NAb) response.

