11.4.4.2 Anti-drug antibodies analysis

The ADA analyses will be performed in the two analysis sets for ADA population as defined in [Section 11.4](#). The baseline value of each applicable ADA variable is the original baseline from the parent study. The incidence of positivity in the ADA assay will be assessed as absolute occurrence (n) and percent of patients (%). Listing of ADA titer levels will be provided for patients positive in the ADA assay. Samples that are positive in the ADA assay will be further characterized for the presence of anti-dupilumab neutralizing antibodies, if applicable. Assessment of the potential impact of ADA on safety, efficacy, and PK may be provided. The ADA analyses will be detailed in SAP.

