2.4 STATISTICAL METHODS

Generalities

For each analysis set defined in [Section 2](#), the planned analyses will be presented by below treatment categories according to the actual treatment groups in the parent study EFC14153:

- Placebo-Dupilumab, defined as the patients who have been in the actual placebo arm of the parent study and exposed to dupilumab in LTS14424.
- Dupilumab-Dupilumab, defined as the patients who have been in the actual dupilumab arm of the parent study and exposed to dupilumab in LTS14424.
- All, defined as all patients from Placebo-Dupilumab and Dupilumab-Dupilumab categories.

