2.4.7 Analyses of Immunogenicity

The baseline value used to define ADA variables is the original baseline from the parent study. The ADA analyses will be performed for each analysis set ([Section 2](#)) of ADA population ([Section 2.3.4](#)) by treatment category.

The ADA variables described in [Section 2.1.6](#) will be summarized using descriptive statistics. Frequency tables of the proportion of patients developing ADA positivity in the ADA assay, neutralizing antibody status in the NAb assay, pre-existing immunoreactivity, treatment-emergent, treatment-boosted, persistent, indeterminate, transient ADA responses and titers will be presented.

Listing of all ADA maximum titer levels and neutralizing antibody status will be provided for ADA positive patients.

ADA variable will be summarized by baseline weight group (≤ 30 , > 30 kg).

If there were patients who had a long gap between the parent EOT visit and the first dose in LTS14424 study, additional analyses excluding such patients may be conducted for the status in the ADA assay in the current study on the full analysis set of ADA population.

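### The parent-study ADA baseline ignores the pre-dose Week 0 sample in former-placebo children, so some reactivity seen before any dupilumab is classed as treatment-emergent and some seen only after it as pre-existing

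*SAP*

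**What the plan says.** **Baseline.** Main SAP 2.1.6: "The baseline used to define ADA variables refers to the baseline value in the parent study". Main SAP 2.4.7: "The baseline value used to define ADA variables is the original baseline from the parent study". Protocol 11.4.4.2: "The baseline value of each applicable ADA variable is the original baseline from the parent study". The three agree, and none makes an exception by parent arm.

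**Classes (SAP 2.1.6).**
- A treatment-emergent response is "a positive response in the ADA assay post first dose in the current study, when baseline status in the parent study is negative or missing".
- A child positive at parent baseline can only be pre-existing or treatment-boosted. One route to pre-existing is "an ADA positive response in the assay at baseline of the parent study with all post first dose ADA results negative in the current study"; the other is that every post-dose titer stays below 4 times the parent-baseline titer. At 4-fold or more the response is boosted.
- The headline classes follow from these: "ADA positive is defined as either treatment-boosted or treatment-emergent response in the ADA assay", and "ADA negative is defined as ADA assay is negative at all times or exhibit a pre-existing immunoreactivity".

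**Groups.** Results are shown by parent treatment. SAP 2.4 defines Placebo-Dupilumab as "patients who have been in the actual placebo arm of the parent study and exposed to dupilumab in LTS14424".

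**The Week 0 sample.** SAP 2.1.6 and the protocol flow chart (section 1.2) schedule an ADA sample at Visit 1, and a flow-chart footnote places it before the injection. SAP 2.1 defines a Week 0 pre-dose value alongside the baseline, and SAP Table 7 gives ADA a Week 0 window. None of the ADA class definitions refers to it.

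**The concern.** For a child who received placebo in the parent study, the last drug-free sample is the one at LTS14424 Visit 1. That visit corresponds to parent Week 52, or later for children who entered late because of COVID-19. The parent baseline is therefore at least about a year older than the first exposure. Assay status can change over that year without any dupilumab, and the rule then assigns the change to the wrong side of first exposure.

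ADA is a named secondary objective (protocol 5.2, SAP 1.2.2), and the class counts are firm outputs of SAP 2.4.7.2. Placebo-Dupilumab is the group in which ADA after first exposure can be observed within this study, so it is the group where the label most needs to be right.

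Other parts of the plan already allow for this:
- SAP 2.4.6.1 has a Week 0 concentration rule specific to former-placebo patients.
- SAP 2.4.5.3 to 2.4.5.5 tabulate laboratory, vital-sign and ECG abnormalities by status at parent baseline and again at Week 0.
- The Japan substudy SAP (3.1) sets the ADA baseline for its dupilumab-naive children at the latest value before the first injection.

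Former-placebo children are equally naive at Week 0, but ADA in the main SAP has no matching rule.

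**Working it through.** The plan states no ADA rate or count, so there is no figure of its own to reproduce. The check is of the classification rule.

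**Step 1. Apply the rule to every pattern.** Three parent-baseline results (negative, missing, positive) × two Week 0 results × four post-dose patterns (all negative; positive below 4-fold; positive at 4-fold or more; negative then positive) give 3 × 2 × 4 = 24 patterns. Each was classed under SAP 2.1.6, then again with the Week 0 sample as baseline. The class differs in 12 of the 24, all of them patterns where parent baseline and Week 0 disagree (missing counted as not positive). Grouped, these are:

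| Parent baseline | Week 0 | After first dose | SAP 2.1.6 | Week 0 as baseline |
|---|---|---|---|---|
| Negative or missing | Positive | Positive, below 4-fold | Treatment-emergent (ADA positive) | Pre-existing (ADA negative) |
| Negative or missing | Positive | Positive, 4-fold or more | Treatment-emergent (ADA positive) | Boosted (ADA positive) |
| Negative or missing | Positive | All negative | No class fits cleanly | Pre-existing (ADA negative) |
| Positive | Negative | Positive, below 4-fold | Pre-existing (ADA negative) | Treatment-emergent (ADA positive) |
| Positive | Negative | Positive, 4-fold or more | Boosted (ADA positive) | Treatment-emergent (ADA positive) |
| Positive | Negative | All negative | Pre-existing (ADA negative) | Neither emergent nor boosted (ADA negative) |

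**Step 2. Count the Week 0-positive patterns.** Of the 12, the SAP classes 6 as treatment-emergent. All 6 have a negative or missing parent baseline and at least one post-dose positive. With the Week 0 baseline, 4 of these become pre-existing and 2 boosted. The other 6 are not treatment-emergent under the SAP: 2 have no post-dose positive, and 4 have a positive parent baseline (3 pre-existing, 1 boosted).

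**Step 3. Count the reverse direction.** With a positive parent baseline and a negative Week 0, 3 patterns become treatment-emergent under the Week 0 baseline: 2 from pre-existing and 1 from boosted.

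These are counts of rule patterns, not patient frequencies. A positive baseline titer was held equal at the two times, so titer drift in children positive at both is not covered.

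**Step 4. Net effect on the headline class.** Let A be former-placebo children in row 1 of the table and C those in row 4. Moving to the Week 0 baseline changes the ADA-positive count by C − A. The documents give neither number, so the sign is unknown.

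**Step 5. Scale of the first direction only, on assumptions.** None of the following is in the documents except 354, the planned enrolment (SAP 1.3):
- former-placebo share one third to one half: 354/3 = 118, 354/2 = 177;
- newly positive at Week 0: 1% to 5%;
- of those, positive after dosing: 50% to 100%.

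Low: 118 × 0.01 × 0.5 = 0.59 children. High: 177 × 0.05 × 1 = 8.85 children. As a share of the group: 0.01 × 0.5 = 0.5 points to 0.05 × 1 = 5.0 points. One child is worth 1/177 = 0.56 to 1/118 = 0.85 points. The percentage range is the product of the assumed inputs and is not evidence that the effect has that size.

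**The case against.** **A single long-term baseline suits an extension study.** It is the SAP's general rule and it matches the protocol. For Dupilumab-Dupilumab this argument stands in full: the parent baseline is the true pre-exposure sample, and an antibody that arose on dupilumab in the parent study is correctly called treatment-emergent. A reader might infer that the rule also misclassifies that group by merging old and new responses. The documents do not support that, because the wording about the current study fixes when the positive sample is taken and does not claim the response first arose then. Separating responses by Week 0 status there would be an optional extra table.

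**The Week 0 result is not lost.** SAP 2.4.7.2 tabulates ADA status and titers by time point and treatment category, so Week 0 positives should be visible. This limits the harm, but the table gives group counts. It cannot show which treatment-emergent children were already positive, and it leaves the classes unchanged.

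**The consequences are limited.** This also stands. The ADA summaries are descriptive, the primary endpoint (treatment-emergent adverse events) is untouched, and the analyses of ADA against safety, efficacy and PK in SAP 2.4.7.3 to 2.4.7.5 are optional.

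**Two further readings go too far.** A reader might infer that any former-placebo child positive at Week 0 is counted as treatment-emergent. The definition also needs a negative or missing parent baseline and a later positive sample. A reader might also infer that Placebo-Dupilumab incidence must be overstated. The reverse pattern works against that, and no rate is given for either.

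**Conclusion.** The concern holds for Placebo-Dupilumab only. The parent-baseline rule misplaces ADA relative to first dupilumab exposure in two specific patterns that pull in opposite directions, and it leaves a child positive only at Week 0 without a clean class. That the rule does this follows directly from the text. How many children it affects does not: the number could be close to zero, and the 0.6 to 8.9 range rests wholly on the assumed placebo share, conversion rate and persistence, and covers one direction only. The point should be corrected because it concerns a named secondary objective, the sample is already scheduled and the change is cheap. It does not threaten the study's main conclusions.

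**What to change.** In main SAP 2.1.6 and 2.4.7, for Placebo-Dupilumab, define the ADA baseline for the pre-existing, treatment-emergent and treatment-boosted classes as the last sample before the first LTS14424 dose, which is the Week 0 pre-dose measurement of SAP 2.1. Keep the parent baseline for Dupilumab-Dupilumab. At minimum, add a sensitivity table of the Placebo-Dupilumab classes on the Week 0 baseline.

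Cost: revised wording and a small derivation change, with no new sample. The two categories would then have different ADA baselines, so the tables and the pooled All column need a footnote. Because the change departs from protocol 11.4.4.2, it should be recorded in SAP 1.6.

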2.1.7 Pharmacodynamic endpoints

2.1.7.1 Whole blood biomarkers

Blood eosinophil counts will be measured as part of laboratory hematology at Visit 1 (Week 0), Visit 3 (Week 4), Visit 5 (Week 12), Visit 8 (Week 24), Visit 9 (Week 36), Visit 10 (Week 52/EOT), Visit 11 (Week 64/EOS) and/or early termination.

2.1.7.2 Serum biomarkers

Serum total IgE and antigen-specific IgE will be measured at Visit 1 (Week 0), Visit 8 (Week 24), Visit 10 (Week 52/EOT), Visit 11 (Week 64/EOS) and/or early termination.

2.2 DISPOSITION OF PATIENTS

This section describes patient disposition for both patient study status and the patient analysis populations for LTS14424 only, unless otherwise specified.

- Screened patients are defined as the patients who signed the informed consent/assent.
- Enrolled patients consist of all the patients who signed the informed consent/assent and had a treatment kit number allocated and recorded in the IVRS/IWRS database, and regardless of whether the treatment kit was used or not.
- The safety population consists of the patients who actually received at least 1 dose or part of a dose of the IMP in the LTS14424 study.

For patient study status, the total number of patients in each of the following categories will be presented in the clinical study report using a flowchart diagram or a summary table:

- Screened patients.
- Screen failure patients and reasons for screen failure.
- Non-enrolled but treated patients.
- Enrolled patients.
- Enrolled but not treated patients.
- Enrolled and treated.
- Patients who did not complete the study treatment period as per protocol.
- Patients who discontinued study treatment by main reason for permanent treatment discontinuation.
- Patients who discontinued from the study.
- Patients who discontinued from the study by main reason for permanent study discontinuation.

Reasons for treatment discontinuation and study discontinuation will be supplied in tables giving numbers and percentages by treatment category as defined in [Section 2.4](#). This summary will be provided by treatment category of each analysis set as defined in [Section 2](#) and may also be further subgrouped by region/pooled countries.

A patient will be considered as lost to follow-up at the end of study if he/she is not assessed at the last protocol planned visit.

All critical or major deviations potentially impacting safety evaluation, drug-dispensing irregularities, and other major or critical deviations will be summarized in tables giving numbers and percentages of deviations by treatment category of each analysis set.

Additionally, the analysis populations for safety, PK and Anti-drug antibody will be summarized in a table by number of patients on the enrolled population.

- Safety population (for both safety and efficacy analyses).
- Pharmacokinetics population.
- Anti-drug antibody population.

2.2.1 Randomization and drug dispensing irregularities

There is no randomization procedure in LTS14424. Drug-dispensing irregularities occur whenever:

- A patient is dispensed an IMP not corresponding to the patient's actual weight, such as
 - a) A patient is dispensed an IMP of 200 mg while patient's actual weight is ≤ 30 kg,
 - b) A patient is dispensed an IMP of 100 mg or 300 mg while patient's actual weight is >30 kg.
- A patient is dispensed an IMP kit not allocated by the IVRS, such as,
 - a) A patient at any time in the study is dispensed a different treatment kit than as assigned,
 - b) A non-enrolled patient is treated with IMP reserved for enrolled patients.

Drug-dispensing irregularities will be monitored throughout the study and reviewed on an ongoing basis.

All drug-dispensing irregularities will be documented in the clinical study report. If the number of irregularities is large enough to make a tabular summary useful, the irregularities will be categorized and summarized among enrolled patients (number and percentages). Non-enrolled and treated patients will be described separately.

Drug-dispensing irregularities to be prospectively identified include but are not limited to:

Drug allocation irregularities

- Kit dispensation without IVRS transaction
 - Erroneous kit dispensation
 - Kit not available
 - Patient enrolled twice
 - Patient switched to another site
-

2.3 ANALYSIS POPULATIONS

The primary analysis population is the safety population. All safety and efficacy analyses will be performed based on the safety population. For each analysis population defined in this section below, the planned analyses will be conducted in two analysis sets: 1) the full analysis set, which will include all data observed in the study 2) the modified analysis set, which will censor the data observed on or after the date of first dose of 300 mg q4w (if applicable) from the full analysis set. Details about the two analysis sets and their corresponding observation periods can be found at the beginning of [Section 2](#).

2.3.1 Safety population

The safety population is defined as all patients exposed to at least 1 dose or part of a dose of the IMP during LTS14424 study regardless of the amount of treatment administered, ie, the exposed population.

Enrolled patients for whom it is unclear whether they took the IMP or not will be included in the safety population as enrolled.

2.3.2 Efficacy population

The efficacy population is the same as the safety population.

2.3.3 Pharmacokinetics (PK) population

The PK population will consist of all the patients in the safety population who had at least 1 non-missing and evaluable predose serum concentration value after the first dose of dupilumab in the LTS14424 study.

2.3.4 Anti-drug antibody (ADA) population

The ADA Population will consist of all the patients in the safety population with at least 1 non-missing ADA result following the first dose of dupilumab in the LTS14424 study.

2.4 STATISTICAL METHODS

Generalities

For each analysis set defined in [Section 2](#), the planned analyses will be presented by below treatment categories according to the actual treatment groups in the parent study EFC14153:

- Placebo-Dupilumab, defined as the patients who have been in the actual placebo arm of the parent study and exposed to dupilumab in LTS14424.
- Dupilumab-Dupilumab, defined as the patients who have been in the actual dupilumab arm of the parent study and exposed to dupilumab in LTS14424.
- All, defined as all patients from Placebo-Dupilumab and Dupilumab-Dupilumab categories.

2.4.1 Demographics and baseline characteristics

The demographics and baseline characteristics will be summarized for each analysis set ([Section 2](#)) of safety population according to the treatment category. The data for demographics and baseline characteristics will be obtained from the original baseline of the parent study. Continuous data will be summarized using the number of available data, mean, standard deviation (SD), median, minimum, and maximum. Categorical and ordinal data will be summarized using the number and percentage of patients.

Parameters described in [Section 2.1.1](#) will be summarized for each analysis set of safety population by the treatment category using descriptive statistics.

Medical and surgical history will be summarized for each analysis set of safety population by the treatment category, by system organ class (SOC) and preferred term (PT) sorted by internationally agreed order of SOC and by the decreasing frequency of PT within SOC based on the overall group. Comorbidity history and atopic medical history will be summarized separately.

2.4.2 Prior or concomitant medications

The prior medications, concomitant medications in parent study, and concomitant medications described in [Section 2.1.2](#) will be presented for each analysis set ([Section 2](#)) of safety population by the treatment category.

Medications will be summarized according to the WHO-DD dictionary, considering the first digit of the anatomic category (ATC) class and the first 3 digits of the ATC class (therapeutic category). All ATC codes corresponding to a medication will be summarized, and patients will be counted once in each ATC category (anatomic or therapeutic) linked to the medication. Therefore patients may be counted several times for the same medication.

The table for prior medications, concomitant medications in parent study, and concomitant medications will be sorted by decreasing frequency of ATC followed by all other therapeutic classes based on the overall incidence across treatment categories. In case of equal frequency regarding ATCs (anatomic or therapeutic categories), alphabetical order will be used.

In addition, the ICS in combination with controller medication(s) and reliever medications will be summarized separately.

